9. STUDY PROCEDURES

9.1 Overview

An Overview of the study visits is shown in **Figure 3**. Eligible Subjects are randomized to iovera[°] treatment or to the standard of care group. The standard of care group treatment consists of all of the standard pre-, peri- and post-operative protocols except that the iovera treatment is not provided. The primary endpoint is cumulative opioid consumption at 6 Weeks Post-TKA.

Figure 3. Overview of Study Visits

*Screening and Treatment can occur on the same day.

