9.4 Randomization

After meeting all of the inclusion and none of the exclusion criteria and prior to study treatment, Subjects will be randomized in a 1:1 manner to either:

- **iovera[°] Treatment:** Subject undergoes treatment with the study device using study supplied Smart Tip.
- **Standard of Care Treatment:** Subject does not undergo iovera[°] Treatment

The Investigator or designee will record the randomization assignment in the source documentation and CRF. Any Investigator who is discovered to tamper with randomization will be immediately terminated from the study.

9.5 iovera[°] Treatment/Visit 2 (5 Days +- 2 days prior to TKA)

Medical history will be reviewed as well as concomitant medications and procedures. Blood pressure and heart rate will be assessed. The Investigator, or designee, will reconfirm all eligibility criteria are met.

The iovera[°] device will be prepared by the trained Investigator (or Sponsor designee) according to the **User Guide**. If at any time the device does not perform as expected the Investigator (or designee) will follow procedures as outlined in the **User Guide**.

Prior to the initiation of the iovera[°] treatment, the Investigator, or designee, will mark the treatment lines on the knee to be treated as shown in Figure 2 located in section 8.2.

Then the skin along the treatment lines will be cleansed with alcohol. Lidocaine, no epinephrine, will be injected along the treatment lines superficially in order to achieve cutaneous anesthesia and to the bottom of the subcutaneous layer, atop the fascia, to temporarily block conduction of the infrapatellar branch of the saphenous nerve and the anterior femoral cutaneous nerve.

Once localized anesthesia of the treatment lines and the nerves is achieved, the Investigator, or designee, will complete the iovera[°] treatment along the treatment lines. Regardless of the length of treatment lines (width of patella or from lower pole of the patella down to tibial tubercle), adjacent insertions are placed along the treatment lines until the entire line has been treated so all Subjects receive the same treatment. Treatment is not to be modified or influenced by any Subject response to changes in knee pain. Representatives of Myoscience, Inc. may be present during the treatment. Photos of the treatment area may be taken.

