11. ADVERSE EVENTS

The study Investigator and Coordinator will evaluate, characterize and record in the CRF all adverse events (AEs) occurring in all subjects from the initiation of study treatment to study exit (or premature withdrawal). Device or procedure related AEs will be followed until resolution. AEs may be reported spontaneously by the subject or detected by the Investigator or coordinator. AEs should be evaluated for diagnoses not just symptoms (i.e., “angina”, not “chest pain”).

AEs may be either spontaneously reported or elicited during questioning and examination of a subject. All AEs must be completely recorded within the Subject's source documentation. All AEs will be evaluated by the Investigator for relationship to the iovera[°] device and to the treatment.

In addition to verbatim terms, the Sponsor will categorize all AEs using MedDRA preferred terms and system organ classes (SOC). Analysis will report both verbatim and MedDRA terms.

Adverse events¹ (AEs) will be assessed continuously from the initiation of study treatment through study exit. Per ISO14155:2011, an AE is any untoward medical occurrence, unintended disease or injury, or untoward clinical signs in subjects, users or other persons, whether or not related to the investigational medical device. An AE can arise from any use of the device (e.g., off-label use, use in combination with any drug) and from any route of administration.

Timely and complete reporting of all AEs assists the Sponsor in identifying any untoward medical occurrence, thereby allowing:

- 1) protection of the safety of study subjects;
- 2) a greater understanding of the overall safety profile of the device;
- 3) recognition of device-related ill effects;
- 4) appropriate modification of study protocols;
- 5) improvements in study design or procedures; and
- 6) adherence to worldwide regulatory requirements.

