### 3.2 Method of Assigning Subjects to Treatment

After meeting all of the inclusion and none of the exclusion criteria and prior to study treatment, subjects will be randomized in a 1:1 manner to either:

- **iovera° Treatment:** Subject undergoes treatment with the study device using study supplied Smart Tip.
- **Standard of Care Treatment:** Subject does not undergo iovera° Treatment

The Investigator or designee will record the randomization assignment in the source documentation and CRF.

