### **6.3 Safety Population**

All subjects who receive study treatment will be included in the Safety Population. Subjects will be analyzed according to the treatment they actually receive, regardless of their randomized treatment. All safety analyses will be based on the Safety Population.

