## **9.0 SAFETY ANALYSES**

All adverse event analyses will be performed on the Safety Population.

The summary of AEs will be limited to treatment emergent AEs. For AEs with a missing start date, the AE will be considered treatment emergent unless there is additional information indicating that the AE started prior to study treatment.

Adverse events (AEs) will be coded using the Medical Dictionary for Regulatory Activities (MedDRA). Treatment-emergent AEs (TEAEs) are defined as any adverse event with onset on or after study treatment begins or any adverse event already present at baseline that worsens in severity. For AEs with missing start dates, the AE will be considered treatment-emergent unless there is additional information indicating that the AE started prior to study treatment. Only treatment emergent AEs will be summarized.

The number and percentage of subjects with at least one TEAE, at least one iovera procedure-related TEAE, at least one iovera device-related TEAE, at least one opioid use related TEAE, at least one serious TEAE, and at least one TEAE leading to study withdrawal will be presented by treatment group. AEs that are definitely, probably, or possibly related, or for which the relationship is missing, will be considered related.

The number and percentage of subjects having a TEAE in each System Organ Class (SOC) and having each individual type of adverse event (Preferred Term) will be presented. TEAEs will also be summarized at the event level by SOC/Preferred Term and severity. This will be done for all TEAEs, iovera procedure related TEAEs, iovera device related TEAEs, and opioid use related TEAEs.

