		95% CI for Mean (1)	(xx.x, xx.x)	(xx.x, xx.x)	
	72 Hours Post-op to 2 Weeks Post-op	n	xx	xx	
		Mean	xx.x	xx.x	xx.x (xx.x, xx.x)
		Median	xx.x	xx.x	
		SD	xx.x	xx.x	
		Minimum - Maximum	xx - xx	xx - xx	
		95% CI for Mean (1)	(xx.x, xx.x)	(xx.x, xx.x)	
	2 Weeks Post-op to 6 Weeks Post-op	...	...	...	...
	6 Weeks Post-op to 12 Weeks Post-op	...	...	...	...
	Hospital Discharge to 2 Weeks Post-op	n	xx	xx	
		Mean	xx.x	xx.x	xx.x (xx.x, xx.x)
		Median	xx.x	xx.x	
		SD	xx.x	xx.x	
		Minimum - Maximum	xx - xx	xx - xx	
		95% CI for Mean (1)	(xx.x, xx.x)	(xx.x, xx.x)	
	Hospital Discharge to 6 Weeks Post-op	p-value (2)			x.xxxx
		...	...	...	...
		...	...	...	...

Program Name:

Creation date, time

Source: Listing 4

Note: Missing pill count data were imputed using multiple imputation methods.

(1) Confidence interval based on the t-distribution.

(2) p-value from a one-sided, two sample t-test, testing the null hypothesis that the true iovera mean is greater than or equal to the true Standard of Care mean versus the alternative hypothesis that the true iovera mean is less than the true Standard of Care mean.

Table 6.1 will be repeated in the following tables:

Table 6.2

OPIOID CONSUMPTION: TOTAL DAILY MORPHINE EQUIVALENT (TME):  
EXCLUDES DISCONTINUATIONS DUE TO ADVERSE EVENTS  
ITT POPULATION

Table 7.1

OPIOID CONSUMPTION: TOTAL DAILY MORPHINE EQUIVALENT (TME)  
PER PROTOCOL POPULATION

Table 7.2

OPIOID CONSUMPTION: TOTAL DAILY MORPHINE EQUIVALENT (TME):  
EXCLUDES DISCONTINUATIONS DUE TO ADVERSE EVENTS  
PER PROTOCOL POPULATION

*Programming note: for Tables 6.2 and 7.2, please add Listing 2.1 to Source.*

Table 8.1

TREATMENT EMERGENT ADVERSE EVENTS (TEAEs): OVERVIEW (SUBJECT LEVEL)  
SAFETY POPULATION

Parameter	OCS (N=xx) n (%)	Standard of Care (N=xx) n (%)
At least one TEAE	xx (xx.x)	xx (xx.x)
At least one iovera procedure-related TEAE (1)	xx (xx.x)	-
At least one iovera device-related TEAE (1)	xx (xx.x)	-
At least one opioid use related TEAE (1)	xx (xx.x)	xx (xx.x)
At least one serious TEAE	xx (xx.x)	xx (xx.x)
At least one TEAE leading to study withdrawal	xx (xx.x)	xx (xx.x)

Program Name:

Creation date, time:

Source: Listing 2.1

Note: Percentages are calculated based on the number of subjects in the ITT Population.

(1) Adverse events that are definitely, probably, or possibly related, or for which the relationship is missing, are considered related.

Table 8.2

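### Table 8.1, the adverse-event overview, is a Safety Population table whose note bases its percentages on the ITT Population; the term *study treatment* also needs a stated meaning for controls

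*SAP*

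**What the plan says.** SAP 6.3 defines the set: "All subjects who receive study treatment will be included in the Safety Population". It continues: "Subjects will be analyzed according to the treatment they actually receive, regardless of their randomized treatment". Protocol 10.3.4 gives the same rule, and SAP 9.0 assigns all adverse-event analyses to this population.

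The Table 8.1 shell is the by-arm overview of treatment-emergent adverse events. It is headed Safety Population. One column is for Standard of Care. The other is evidently for iovera but is labelled OCS, which is not in the SAP's abbreviation list. The note under the table reads: "Note: Percentages are calculated based on the number of subjects in the ITT Population".

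On timing, SAP 9.0 counts as treatment-emergent "any adverse event with onset on or after study treatment begins", plus pre-existing events that worsen. Protocol 11 covers events "occurring in all subjects from the initiation of study treatment to study exit (or premature withdrawal"). Neither document defines *study treatment*. The schedules (Protocol Table 2, SAP Table 1) mark it at Visit 2 only, the iovera visit. For the control arm, Protocol 9.4 says "Subject does not undergo iovera[°] Treatment", and Protocol 9.1 describes the standard pathway "except that the iovera treatment is not provided".

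**The concern.** Table 8.1 is where a reader will look first for the share of subjects in each arm with any event, a serious event or an event leading to withdrawal. Under its heading, the numerator comes from the Safety Population by treatment received. Under its note, the denominator comes from everyone randomised. The two need not match. A randomised subject outside the safety set sits in the denominator but cannot appear in the numerator. A subject who crosses over sits in one group's numerator and in the other group's denominator. The overview could then disagree with the detailed tables that follow it.

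The second matter is a gap. A programmer has no written rule for what admits a control to the Safety Population, or for the date from which a control's events are treatment-emergent. This may reach data capture as well. The footnote to Protocol Table 4 treats changes in condition between Screening and the start of study treatment as medical history. The assumed start for a control therefore decides whether a pre-operative event is an adverse event at all.

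**Working it through.** **Step 1. Denominators side by side.** All the adverse-event table shells are headed Safety Population.

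- Table 8.1 (subject level): the ITT number.
- Tables 8.2, 9.1, 9.3 and 9.5 (subject level): N of the treatment group.
- Tables 8.3, 9.2, 9.4 and 9.6 (event level): the number of events with non-missing severity.

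Table 8.1 alone names the ITT Population, and this conflicts with its own heading and with SAP 6.3 and 9.0.

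**Step 2. Can the two sets differ?** The SAP allows for it. Listing 1, run on the ITT Population, has a column for Safety Population membership and a programming note to flag subjects whose actual group is not the randomised one. Table 16 has a row for incomplete iovera treatment.

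**Step 3. Size.** The documents give no adverse-event counts, number untreated or number crossing over, so there is no plan figure to reproduce. The one input from the plan is about 60 randomised per arm (SAP 3.4, Protocol 10.8). The rest is assumed.

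For e subjects with an event, the correct percentage is 100 × e / N(safety) and the printed one is 100 × e / N(ITT). The ratio of printed to correct is N(safety) / N(ITT).

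For scale, the plan raises 114 subjects to 120: 120 − 114 = 6, or about 3 per arm, and 60 − 3 = 57. That allowance is for early withdrawal and missing primary-endpoint data, not for untreated subjects, so 57 is only an assumption of plausible size.

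| Outside the safety set, of 60 | Subjects with an event | Correct | Printed | Shift (points) |
|---|---|---|---|---|
| 0 | 12 | 12/60 = 20.0% | 20.0% | 0 |
| 3 | 11 | 11/57 = 19.3% | 11/60 = 18.3% | 1.0 |
| 3 | 12 | 12/57 = 21.1% | 20.0% | 1.1 |
| 3 | 30 | 30/57 = 52.6% | 30/60 = 50.0% | 2.6 |
| 6 | 30 | 30/54 = 55.6% | 50.0% | 5.6 |

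Crossover, assuming 3 subjects randomised to iovera are treated as controls: the as-treated sizes are 60 − 3 = 57 and 60 + 3 = 63. With 12 subjects having an event in each as-treated group, the correct figures are 12/57 = 21.1% and 12/63 = 19.0%. Table 8.1 would print 20.0% for both. Here the iovera figure is understated and the control figure overstated.

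**Step 4. The term for controls.** The schedule ties *study treatment* to the iovera visit, and controls do not receive iovera. No other passage gives their entry event or start date. The only number available is conditional. Iovera is given 5 ± 2 days before surgery, so 3 to 7 days, and follow-up runs 12 weeks, or 84 days. If controls were started at surgery, the iovera window would be 87 to 91 days against 84, longer by 3/84 = 3.6% to 7/84 = 8.3%. Nothing in the documents says controls are to be started there.

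**The case against.** The Table 8.1 note looks like a template slip, as does the OCS header above it. SAP 6.3 and 9.0 state the right rule, four other subject-level tables are consistent with it, and SAP 9.0 plans no hypothesis test on adverse events. If everyone receives the assigned arm, the two denominators are equal. All of that stands and limits the size of the point. It does not remove the contradiction, because the shell note is what gets programmed and printed.

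On the control arm, a reader might infer that controls fall outside the Safety Population, so that their column would have N = 0. The documents do not support this. They name the control option "Standard of Care Treatment" and place randomisation of both arms before study treatment. Protocol 11 records events in all subjects. Tables 8.1, 8.2 and 9.5 have control columns, and Tables 8.3 and 9.6 are continued for controls. Inclusion of controls is the evident intent.

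A reader might also infer that the iovera arm is observed 3 to 7 days longer. That follows only if someone starts controls at surgery. The schedules are not arm-specific and mark adverse-event assessment at Visit 2, and nothing legible says controls skip that visit. Protocol Figure 3, the visit overview, could not be read here and may show it. The 3.6% to 8.3% is also extra observation time, not a shift in event percentages.

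**Conclusion.** The Table 8.1 note is wrong as written. It contradicts the table's own heading and SAP 6.3 and 9.0, and it disagrees with Tables 8.2, 9.1, 9.3 and 9.5. The error is confined to that one table. Its effect is nil if all randomised subjects receive their assigned arm, about one percentage point in the 57-of-60 illustration with 11 events, and up to 5.6 points in the most extreme case tabulated. These sizes rest on assumed counts.

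The control arm's safety set and event window are undefined, not shown to be wrong. That part calls for clarification and supports no claim of biased observation time.

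**What to change.** Change the Table 8.1 note so that percentages use the number of Safety Population subjects in each group by treatment received, and change the OCS header to iovera.

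In SAP 6.3, state which event brings a control subject into the Safety Population. In SAP 9.0, give a comparable start of adverse-event and treatment-emergent counting for both arms, for example the Visit 2 date or a matching pre-operative date for controls. Read Protocol 10.4.4 and 11 the same way.

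Keep events after the iovera procedure in the safety tables. A tempting alternative is to admit anyone who receives iovera or has surgery and then count onset only from surgery in both arms. That would leave an iovera subject whose surgery is cancelled in the denominator with no way to contribute an event. It would also move the first days after the procedure out of the between-arm table.

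The cost is one note, one header and a few sentences in the SAP. If sites filed pre-operative events in controls as medical history, those records would need checking against the chosen start.

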## 7.0 DEMOGRAPHICS

Subject demographics collected at the screening visit will be summarized using descriptive statistics for continuous variables (age at informed consent) and frequencies and percentages for categorical variables (gender, ethnicity, and race).

## 8.0 EFFECTIVENESS ANALYSES

### 8.1 Primary Effectiveness Endpoint

The primary effectiveness endpoint is the cumulative consumption of opioids from the time of hospital discharge to 6 weeks post-TKA Surgery. Opioid consumption will be converted to morphine equivalents (see Appendix 2 for conversion factors), and subject consumption will be verified by pill count at follow-up visits. The cumulative morphine equivalent will be divided by the number of days to provide the Total Daily Morphine Equivalent (TME) for the subject.

The difference in the mean TMEs between the two treatment groups will be calculated as Standard of Care TME mean – Active TME mean, such that a positive difference indicates that the Standard of Care Treatment group had a larger mean TME than the Active Treatment group, while a negative difference indicates the opposite. A positive difference between the two treatment groups reflects a positive outcome for the study.

Let  $\mu_{1,Active}$  and  $\mu_{1,SOC}$  denote the true mean TMEs for the active and standard of care treatments, respectively. Then the null and alternative hypotheses for the primary effectiveness endpoint are as follows:

$$H_0: \mu_{1,Active} \geq \mu_{1,SOC}$$

$$H_1: \mu_{1,Active} < \mu_{1,SOC}$$

Missing data for this endpoint will be imputed using multiple imputation methods. First, the relatively uncommon, non-monotone missing data will be imputed using the MCMC option of SAS® PROC MI. For this endpoint, the imputation model will include a term for treatment and the pill counts at visits 4, 5, and 6. Second, the monotone missing values will be imputed using the chained equation method by SAS® PROC MI option MONOTONE REG. For each subject within each imputed dataset, the value of the endpoint will then be determined. The imputed data sets will each be analyzed to obtain the difference in means between treatments and the corresponding standard error, and the results will be summarized using PROC MIANALYSE. A one-sided t-test will be used to test the null hypothesis. The Primary Effectiveness Study Objective will be met if this t-test is statistically significant using a  $\alpha = 0.025$  level of statistical significance.

This endpoint will be summarized by treatment group using descriptive statistics, together with 95% confidence intervals for the true mean based on the t-distribution. The estimated difference in mean TMEs between the two treatment groups and a 95% confidence interval based on the t-distribution for the true difference in the mean TMEs between the two treatments will also be provided.

TME data will be summarized in the same manner for other time periods (TKA to 72 hours post-op, 72 hours post-op to 2 weeks post-op, 2 weeks post-op to 6 weeks post-op, 6 weeks post-op to 12 weeks post-op, hospital discharge to 2 weeks post-op, hospital discharge to 6 weeks post-op, and hospital discharge to 12 weeks post-op), but no hypothesis testing will be performed.

These analyses will be performed for the ITT Population and the Per Protocol Population.

For each population, an additional analysis of TME data will be performed excluding subjects that discontinued the study due to adverse events.

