The total number of outpatient Physical Therapy visits conducted between each study visit will also be obtained. Additional Data collected from Physical Therapy Visits will include:

- Pain while seated

Subjects will be asked to bring all prescription opioid bottles to all study follow-up visits. A pill count will be completed by the study coordinator, or designee, and opioid medication will be redisensed to subjects.

At the completion of this visit, the Subject will be exited from the study unless the Subject has any ongoing device-related or iovera^o treatment-related adverse events as described in section 10.8.

Table 2. Schedule of Assessments

Assessment	Visit 1 / Screening	Visit 2 / Iovera [®] Treatment	Visit 3 / DAY OF TKA (Day 0)	Visit 4 / 72 Hours Post-op	Visit 5 / 2 Weeks Post-op	Visit 6 / 6 Weeks Post-op	Visit 7 / 12 Weeks Post-op
Informed Consent	X						
Eligibility	X	X					
Medical history	X	X					
Concomitant medication assessment	X	X	X	X	X	X	X
Prior/Concurrent Therapy	X	X		X	X	X	X
Randomization*	X						
Study Treatment		X					
Physical Exam	X						
Vital signs	X	X					
Knee Circumference	X						
KOOS JR. Questionnaire	X			X	X	X	X
NRS for Pain	X			X	X	X	X
Subject Satisfaction Questions						X	X
Physical Performance Measures	X				X	X	X
Pain Medication Accountability				X	X	X	X
AE/SAE Assessment		X	X	X	X	X	X

* Randomization occurs after the subject has met eligibility criteria

Follow-up visits generally consist of the following:

- The Investigator or designee assesses the occurrence of health status changes and adverse events since last study visit;
- The Investigator or designee determines whether any changes in daily medications have occurred;
- The Investigator or designee performs drug accountability (pill counts) of post-operative outpatient opioid medication and re-dispenses unused opioid medications to subjects after use. The Investigator or designee records other over-the-counter concurrent pain medication use and pain relief therapies used per subject report;
- The Subject completes a KOOS JR. questionnaire, [REDACTED] Satisfaction questions (Visit 6 and 7 only), and reports NRS for Pain when standing from a seated position;
- The Investigator or designee performs Physical Performance Measures ([REDACTED] Get Up and Go Test).

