Let  $\mu_{2,\text{Active}}$  and  $\mu_{2,\text{SOC}}$  denote the true mean AUC/time based on the Change from Baseline in KOOS JR. score from the Baseline visit through the six-week visit for the active and standard of care treatments, respectively. Then the null and alternative hypotheses for the test for non-inferiority for this endpoint are as follows:

$$H_0: \mu_{2,\text{SOC}} - \mu_{2,\text{Active}} \geq \delta$$

$$H_1: \mu_{2,SOC} - \mu_{2,Active} < \delta,$$

where the non-inferiority margin  $\delta=14$ .

Missing KOOS JR. data will be imputed using multiple imputation methods. First, the relatively uncommon, non-monotone missing data will be imputed using the MCMC option of SAS® PROC MI. The imputation model will include a term for treatment and the KOOS JR. score at visits 1, 4, 5, and 6. Second, the monotone missing values will be imputed using the chained equation method by SAS® PROC MI option MONOTONE REG. For each subject within each imputed dataset, the value of the endpoint will then be determined. The imputed data sets will each be analyzed to obtain the difference in means between treatments and the corresponding standard error, and the results will be summarized using PROC MIANALYZE (with THETA0=14, the non-inferiority margin, in the PROC MIANALYZE statement). The null hypothesis will be tested using a one-sided t-test. One of the secondary objectives of the study is to show that, over the 6-week post-TKA period, the Active Treatment group has similar levels of pain and functioning as compared to the Standard of Care Treatment group. This objective will be met if the t-test for non-inferiority is statistically significant using a 0.025 level of statistical significance.

There is one item in the KOOS JR. scale (Knee Twisting/Pivoting) with a large number of missing responses. Prior to undergoing multiple imputation, missing values for this item will be imputed by performing a linear regression (SAS PROC GLM) on the other 6 KOOS JR. items and imputing the Knee Twisting/Pivoting score for each patient with a missing value based on the estimated linear regression line. At baseline this imputation will be performed across treatment arms; at post-baseline time points the imputation will be performed by treatment arm.

Change in NRS for Pain scores and TUG test scores from the Baseline visit to each post-baseline visit will be calculated for each subject as:

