#### **8.4 Other Analyses**

AUC/time based on Changes from Baseline in KOOS JR. Scores, NRS for Pain, and TUG test through 72 hours post-TKA (KOOS JR. and NRS for Pain only), 2 weeks post-TKA and 12 weeks post-TKA will be analyzed in the same manner as described in Section 8.2 for the AUC/time endpoints through 6 weeks post-TKA. AUC/time based on Changes from Baseline in ROM through 2 weeks post-TKA, 6 weeks post-TKA, and 12 weeks post-TKA will also be analyzed in this same manner.

Subject satisfaction data will be summarized by treatment group and visit (weeks 6 and 12) using descriptive statistics for both overall knee pain status since the beginning of the study and satisfaction with pain management following surgery and counts and percentages for overall knee pain status since the beginning of the study.

██████████ last NRS for Pain (both seated and with motion) reported as part of physical therapy will be summarized by treatment group using descriptive statistics.

For each post-baseline visit, p-values will be presented for the test of the null hypothesis that the true mean changes from baseline in NRS for Pain are equal for the two treatments versus the alternative hypothesis that they are not equal. It should be noted that this is an open label study and that these hypothesis tests of superiority are post-hoc and were not pre-planned in the protocol.

These analyses will be performed for the ITT Population.

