(2) p-value from a two-sided, two-sample t-test, testing the null hypothesis that the iovera and Standard of Care means are equal versus the alternative hypothesis that they are unequal.

(3) p-value from a two-sided, paired t-test, testing the null hypothesis that the true mean equals 0.

(4) p-value from a one-sided, two-sample t-test, testing the null hypothesis that the iovera mean is less than or equal to the Standard of Care mean versus the alternative hypothesis that the iovera mean is greater than the Standard of Care mean.

Table 3

KOOS JR.  
ITT POPULATION

Parameter	Visit	Statistic	Iovera (N=xx)		Standard of Care (N=xx)		Difference in Mean Change from Baseline (Iovera - Standard of Care) and 95% CI (1)
			Value	Change from Baseline	Value	Change from Baseline	
Overall Score	Screening (Baseline)	n	xx		xx		
		Mean	xx.x		xx.x		
		Median	xx.x		xx.x		
		SD	xx.x		xx.x		
		Minimum - Maximum	xx - xx		xx - xx		
	72 Hours Post-op	95% CI for Mean (1)	(xx.x, xx.x)		(xx.x, xx.x)		
		n	xx	xx	xx	xx	
		Mean	xx.x	xx.x	xx.x	xx.x	xx.x (xx.x, xx.x)
		Median	xx.x	xx.x	xx.x	xx.x	
		SD	xx.x	xx.x	xx.x	xx.x	
	2 Weeks Post-op 6 Weeks Post-op 12 Weeks Post-op	Minimum - Maximum	xx - xx	xx - xx	xx - xx	xx - xx	
		95% CI for Mean (1)	(xx.x, xx.x)	(xx.x, xx.x)	(xx.x, xx.x)	(xx.x, xx.x)	
		...	...	...	...	...	...
		...	...	...	...	...	...
		...	...	...	...	...	...
AUC/time for Change from Baseline in Overall Score	Baseline through 72 Hours Post-op	n	xx		xx		
		Mean	xx.xx		xx.xx		xx (x.x, x.x)
		Median	xx.xx		xx.xx		
		SD	xx.xx		xx.xx		
		Minimum - Maximum	xx.x - xx.x		xx.x - xx.x		
	Baseline through 2 Weeks Post-op 6 Weeks Post-op 12 Weeks Post-op	95% CI for Mean (1)	(xx.xx, xx.xx)		(xx.xx, xx.xx)		
		p-value (2)	x.xxxx		x.xxxx		
		p-value (3)				x.xxxx	
		...	...	...	...	...	...
		...	...	...	...	...	...

Program Name:

Creation date, time

Note: Change from baseline = Post-baseline value - Baseline value, so that a positive change value indicates a positive outcome. Missing overall scores were imputed using multiple imputation methods.

Koos JR. normalized scores range from 0 (extreme symptoms) to 100 (no symptoms).

(1) Confidence interval based on the t-distribution.

(2) p-value from a two-sided, paired t-test, testing the null hypothesis that the true mean equals 0.

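### The imputation of a missed 6-week opioid count leaves out the Visit 7 tablet record, which caps the missing value and sometimes fixes it

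*SAP*

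**What the plan says.** SAP 8.1 sets the model for the primary endpoint: "For this endpoint, the imputation model will include a term for treatment and the pill counts at visits 4, 5, and 6". SAP 5.3 and Protocol 10.5 give the same list as an example. Non-monotone gaps go to the MCMC step and monotone gaps to MONOTONE REG. No limits on the drawn values are stated. For KOOS JR., SAP 8.2 says: "The imputation model will include a term for treatment and the KOOS JR. score at visits 1, 4, 5, and 6".

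Visit 7 data are collected. Protocol 9.7 says of the 12-week visit: "A pill count will be completed by the study coordinator, or designee, and opioid medication will be redisensed to subjects". The schedules in both documents mark medication accountability and KOOS JR. at that visit. Listing 4 has columns for tablets newly acquired, tablets re-dispensed at the last visit and tablets remaining. SAP 5.4 runs the analyses on the final locked database, so the Visit 7 record is to hand when the imputation is done.

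Twelve-week results are also planned. SAP 8.1 says: "TME data will be summarized in the same manner for other time periods", and its list ends with "hospital discharge to 6 weeks post-op, and hospital discharge to 12 weeks post-op". SAP 8.4 says of the KOOS JR. AUC/time results: "2 weeks post-TKA and 12 weeks post-TKA will be analyzed in the same manner as described in Section 8.2". The shells of Tables 6.1 and 3 carry notes that apply to every row: "Missing pill count data were imputed using multiple imputation methods" and "Missing overall scores were imputed using multiple imputation methods".

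**The concern.** Cumulative consumption cannot fall. If a subject misses Visit 6 and returns at Visit 7, the tablets used between Visits 5 and 7 set an upper limit on what was used between Visit 5 and week 6. If none were used, the 6-week total equals the Visit 5 total and nothing is missing.

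A model confined to Visits 4 to 6 cannot see this. To it, the subject looks like a dropout after Visit 5, so MONOTONE REG draws the Visit 6 count from the earlier counts plus residual noise. The draw may imply a 6-week total above the recorded 12-week total. That subject's 6-to-12-week consumption would then be negative in Table 6.1, while Listing 4 shows the observed figure.

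The primary ITT analysis would thus carry avoidable error in a few subjects. The Per-Protocol analysis is untouched on this point, because SAP 6.2 requires a completed 6-week visit.

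**Working it through.** **1. The plan's own sample size.** Inputs from SAP 3.4: difference 12.0 mg, SDs 18.2 and 26.0, one-sided 0.025, Satterthwaite t-test. With n per group, λ = 12/√[(18.2² + 26.0²)/n], df = (n−1)(18.2² + 26.0²)²/(18.2⁴ + 26.0⁴), and power is the upper tail of the noncentral t beyond its critical value. The smallest n reaching 80% is 56. At n = 57, λ = 12/√(1007.24/57) = 2.855, df ≈ 100, and power is 80.7%. The stated 57 is consistent with that.

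**2. The cap from Visit 7.** Use between Visits 5 and 7 is

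U = Σ over drugs of (re-dispensed at Visit 5 + newly acquired − remaining at Visit 7) × MME per tablet.

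The 6-week total lies between the Visit 5 total and the Visit 5 total + U. On the TME scale the width is U/days. I assume 42 days. The endpoint starts at discharge, so the true divisor is somewhat smaller; 40 days would raise each width below by 5%.

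MME per tablet uses the strengths in Protocol 9.6 and the factors in SAP Appendix 2: oxycodone 5 × 1.5 = 7.5; tramadol 50 × 0.1 = 5. The initial supply is 40 × 7.5 + 40 × 5 = 300 + 200 = 500 MME.

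| Use between Visits 5 and 7 (assumed examples) | U (MME) | Width (mg/day) |
|---|---|---|
| None, no refill | 0 | 0 (value known) |
| 5 oxycodone tablets | 37.5 | 0.89 |
| 20 oxycodone and 20 tramadol tablets | 250 | 5.95 |
| Whole initial supply, no refill | 500 | 11.9 |

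Example: with 200 MME used by Visit 5 and still 200 at Visit 7, the 6-week TME is 200/42 = 4.76 mg/day. With five oxycodone tablets used in between, it lies between 4.76 and 237.5/42 = 5.65.

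**3. Noise in one imputed value.** The residual SD is SD × √(1 − ρ²), where ρ is the correlation between the missing value and its predictors. The documents do not give ρ. For assumed values of 0.80 to 0.95, it is 10.9 to 5.7 mg/day for iovera and 15.6 to 8.1 for standard of care. One such subject among 60 moves the arm mean by at most about 15.6/60 = 0.26 mg/day (one SD), against a planned difference of 12.

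**4. How many subjects, and how much power.** The plan's allowance is 120 − 114 = 6 subjects. If half of them miss Visit 6 but attend Visit 7 (assumption), that is 3; the range within the allowance is 0 to 6. As an upper limit, treat affected subjects as lost outright, split evenly between arms:

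| Subjects lost | Power, SAP SDs |
|---|---|
| 0 (60 per group) | 82.7% |
| 2 | 82.1% |
| 3 | 81.7% |
| 6 (57 per group) | 80.7% |

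With the protocol's iovera SD of 16.9 (Protocol 10.8), the fall from 0 to 6 is from 84.4% to 82.4%, again about 2 points.

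**The case against.** The best defence is that imputation is for missing data, and nothing forbids a programmer from deriving a value that the accountability records already settle. The cap is also often loose: at 11.9 mg/day it is about as wide as the planned effect, and refills can widen it further. Tablet counts depend on subjects bringing every bottle, and Listing 4 has a column for discrepancies, so fixing a value from Visit 7 brings its own assumption. Limits that differ by subject are not part of the MCMC and MONOTONE REG steps as specified. The effect is small, and no direction of bias is shown.

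All of this limits the size of the point and shapes the remedy. It does not remove the point: SAP 8.1 names the visits for this endpoint, Visit 7 is not among them, and no derivation rule is given.

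A reader might also infer that the 12-week rows of Tables 3 and 6.1 must be complete-case results under a false note. The documents do not support that. The visit lists in SAP 8.1 and 8.2 describe the 6-week endpoints, and the wording for other periods can be read as the same procedure with that period's visits. What is missing is a named 12-week model. Those rows carry no confirmatory weight: SAP 8.1 plans no tests for the other TME periods, and the 12-week KOOS JR. result is among the other analyses, outside the fixed sequence.

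**Conclusion.** The point holds as a modest defect in the primary imputation. Followed literally, SAP 8.1 draws a missed 6-week value without a record that caps it and, with no later use and complete records, determines it. Impossible totals are not ruled out.

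The number affected is unknown: about 3 subjects under the stated assumption. At most about 2 points of power are at stake within the six-subject allowance. It would be wrong to conclude that the sample size is threatened, that the primary result is biased in a known direction, or that Visit 7 settles every missed Visit 6. The change is worth making because the data are already collected. For the 12-week rows, only a clarification is needed.

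**What to change.** In SAP 5.3 and 8.1:

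- Before imputation, derive the missed Visit 6 value when complete accountability records show no use between Visits 5 and 7.
- Otherwise, add Visit 7 opioid use to the imputation model and keep imputed 6-week cumulative use between the observed Visit 5 and Visit 7 totals. One way is to impute the share of the Visit 5-to-7 use that falls before week 6.
- Do not apply the derivation or the limits where bottles or refill records are incomplete or discrepant.

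In SAP 8.2, add Visit 7 KOOS JR. to its model. The extended models then also serve the 12-week rows of Tables 3 and 6.1. Alternatively, limit the two table notes to the rows actually imputed.

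The cost is slightly more programming and reliance on complete bottle and refill records. No new data are needed, and there is no delay, since SAP 5.4 already waits for the final lock. The internal soft-lock analysis in Protocol 10.4.1 may come before some Visit 7 counts, so its imputed values may differ; the SAP should say that the final-lock analysis governs.
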